7.2.2 Exclusion Criteria

Subjects who meet any of the exclusion criteria described below will not be eligible for this clinical investigation.

- 1) Subjects with single-sided deafness (SSD).
- 2) Subjects who are not affiliated to the French Social Security.
- 3) Subjects who are under legal protection.

7.2.3 Number of Subjects Required

For a test battery that has an underlying moderate specificity and sensitivity of ~80%, a total of 30 subjects should be sufficient to conclude that there is a relationship between pass/fail outcome of the battery (cumulatively – fail on any test -> fail) and good/poor performance based on sentence test score criterion. Therefore, we aim to recruit 30 or more subjects.

The sample size calculation is to be found in section 9.3.1.

All patients implanted since the centre started using their specific test battery will be screened for eligibility. The centre's staff currently estimate that 30 or more patients are eligible.

7.2.4 Vulnerable Populations

Not applicable.

7.2.5 Recruitment and Study Duration

The following subject status definitions apply:

- *Enrolled*: A subject who is has not opposed to participation in the study.
- *Screen Fail*: An Enrolled subject that has been determined to not meet one or more eligibility criteria.
- *Participated*: Has provided answers to the patient questionnaire.
- *Withdrawn*: Not applicable.
- *Completed*: Enrolled subjects who completed the patient questionnaire.

The recruitment period for the clinical investigation is estimated to be approximately 3 months from the time of first subject enrolled to the last subject.

Recruitment of subjects shall be performed in a back-chronological order from the cochlear implantation surgery. Recruitment shall start with the last subject that has undergone this procedure in the year 2021 and chronologically working backwards until recruitment targets are met.

This process will avoid any recruitment bias.

The expected duration of each subject's participation in the clinical investigation is the time it takes for the subject to read and discuss the non-opposition form with the study team, complete and return the questionnaire. Time for completing the questionnaire is estimated to be 30-40 minutes.

Clinical Investigation completion is defined as the recording and completion of the last medical record search for the last enrolled subject in the electronic Case Report Forms (eCRF).

7.2.6 Criteria for Subject Withdrawal

Subjects can decide to withdraw from the investigation at any time. The Investigator shall ask the reason(s). The reason for withdrawal should be documented in the subject's source files and the case report form (CRF).

Participating subjects who are withdrawn/discontinued will be replaced.

7.2.7 Randomisation Procedures

Not applicable.

7.2.7.1 Blinding Procedures

Not applicable.

7.2.8 Post-investigation Medical Care

The study is non-interventional. Subjects will continue to receive standard care from the centre and no specific care will be provided for the subjects after this study has been completed.

7.3 Performance Evaluations and Procedures

7.3.1 Eligibility and Informed non-opposition form

Screening of subjects include searches by site personnel in medical records for inclusion and exclusion criteria. Eligible subjects will be included based on date of cochlear implant surgery, from most recent to least recent. In a first draw, the number of subjects intended to be enrolled plus 20% (to account for non-responders) will be contacted.

Eligible subjects will be contacted by the investigator regarding the investigation. If they agree to receive a non-opposition form, this will either be sent to them by mail or shared directly at the clinic if they are scheduled for an appointment. Subjects will be given sufficient time to read the non-opposition form, ask questions and have those questions answered by the site personnel responsible for non-opposition process. If the subject is not opposed to participate, the date of the discussion will be documented in the subject's medical records and in the non-opposition form and will be used as the date of enrolment. A copy of the non-opposition form, signed by the investigator, will be shared with the subject together with the questionnaire.

When a subject is enrolled in the investigation, data collection can start. In case subjects are due for a follow-up appointment at the clinic, as per standard of care, the questionnaire can be completed at site. For those subjects where a visit at the clinic during the investigation period is not scheduled, the questionnaire (together with a copy of the non-opposition form signed by the investigator) will be sent via mail to be completed at home. All questions regarding the questionnaire can be raised with the site personnel. If completed at home, the questionnaire shall be sent back to the clinic by registered mail using a pre-filled and stamped envelope with the address of the clinic.

The completeness of the questionnaire will be verified by site personnel. Incomplete data will be followed-up with the subject, if answered at home by sending a copy of the questionnaire back to the subject where incomplete parts requiring an answer are highlighted.

If the questionnaire is not returned; every possible effort must be made by the study site personnel to contact the subject and determine the reason for discontinuation. At least 3 separate attempts taken to contact the subject must be documented.

The subjects will be asked to complete the following questionnaire: Speech, Spatial and Qualities of Hearing Scale (SSQ-12 version).

7.3.2 Self-reported performance (at time of recruitment)

The SSQ12 questionnaire will be used. The Speech, Spatial, and Qualities of Hearing Scale questionnaire (SSQ-12) (Noble et al, 2013) was developed in the MRC Institute of Hearing Research, UK, and is a scaled-down version of the 49 items SSQ questionnaire (Gatehouse & Noble, 2004). It is designed to compile a sub-set of items from the longer original 49 version to represent the scale as a whole, measuring self-reported auditory disability, reflecting the reality of hearing in the everyday world. It has been shown to provide similar results to SSQ-49 (Noble et al, 2013). It covers:

- Hearing speech in a variety of competing contexts
- The directional, distance and movement components of spatial hearing
- Segregation of sounds and attending to simultaneous speech streams
- Ease of listening
- The naturalness, clarity and identifiability of different speakers, different musical pieces and instruments, and different everyday sounds.

7.3.3 Retrospective study data collected from medical records

7.3.3.1 Demographic information

Demographic, hearing history, device information and general medical history will be collected from the centre's files once written informed non-opposition has been received. Comorbidities and concomitant prescription medications or therapies from activation to 1-month as reported to the clinician.

7.3.3.2 Pre-operative and intra-operative data

Surgical and imaging parameters from reports. Pre-op AC & BC audiograms, if available. Pre-op Fournier monosyllable test score in quiet (presented at 60 dB SPL).

7.3.3.3 Device parameters

The centre will provide anonymised data collected from the Nucleus CustomSound programming system "CDX" data files: This will include threshold and comfortable stimulation levels used in sound processors, and other sound processor parameters and data logging. All ECAP bottom-up processing test data are also stored in CDX data file (next section 7.3.3.4).

7.3.3.4 ECAP-based bottom-up tests (post-surgery)

Specific ECAP-based standard tests of bottom-up processing were established at the centre. Firstly, automatic ECAP thresholds using "AutoNRT" are measured for each intracochlear electrode using default parameters. Then one basal electrode (number 8) and one apical electrode (16) is used for subsequent tests. If there is no AutoNRT response on one of these electrodes, then an adjacent one

is used. All subsequent ECAP testing uses the forward masking artifact reduction technique with equal masker and probe levels.

Firstly, a negative-leading AGF is measured up until 220 CL or the subject indicates that the sound is too loud. Then an AGF is measured using the positive-leading polarity pulses.

The CL to obtain 100 μ V is determined from the standard AGF, or the maximum tolerable CL if 100 μ V was not obtained. This CL is used for subsequent recovery function and SOE tests.

Recovery functions are obtained using a standard sequence of masker-probe intervals and the CustomSound EP software computes the absolute and relative refractory periods.

SOE functions are obtained using a specific sequence of maskers so reduce overall test time. The maskers span 14 electrode locations but not all locations are used. The CustomSound EP software computes the 50% maximum amplitude width (in electrodes). The area under the curve can be computed manually (up to 14 electrode units).

7.3.3.5 Functional cognitive tests (post-surgery)

MoCA test score and number of words given in fluency subtest; raw Stroop subtest scores and number of noted errors; ÉCLA-16+ subtest 3 and 4 scores and completion times will be collected. Tests can have been performed at any time post-surgery.

7.3.3.6 Post-operative audiometric data

Aided sound-field warble-tone thresholds (dB HL: 250, 500, 1000, 2000, 4000 Hz) performed soon after activation will be collected.

The Toulouse centre presents sentence material at 65 dB SPL in quiet and in 8-talker babble presented in front from the same speaker. French MBAA2 sentence recognition scores (/100, single list per condition) will be collected for the implant ear alone where performed:

- In quiet at 1-day
- In quiet at 1-month
- 10 dB SNR at 1-month (or verify as zero)
- 5 dB SNR at 1-month (or verify as zero)

French MBAA dB SNR50 at 1-month (or verify non-convergent or score in quiet <80/100) will be collected. The SNR50 is derived from several fixed-SNR test scores using logistic interpolation.

7.3.3.7 Long-term sentence recognition scores (up until time of recruitment)

French MBAA sentence recognition scores in quiet and in noise the implant ear alone will be collected where performed between one-month post-activation and the time of recruitment. Logistic interpolation may be used to obtain scores for missing test levels or SNR50 (data analysis stage). Dates of tests will also be collected to enable longitudinal extrapolation.

7.4 Safety Evaluations and Procedures

Not applicable. Non-interventional study.

7.4.1 Concomitant Medication and Therapies

Not applicable.

7.5 Equipment Used for Evaluation of Performance and Safety

No special equipment required.

7.6 Sponsor Role in Conduct of the Clinical Investigation

The Sponsor employees (or designee) shall use standard operating procedures to ensure that clinical study procedures and documentation are consistently conducted and compliant with Declaration of Helsinki and applicable parts of GCP and any regional or national regulations.

The Sponsor shall ensure that the study is quality controlled (monitored) by a monitor who is independent from the study, scientifically and clinically competent and has good knowledge of the study plan, non-opposition process, sponsor's SOPs, GCP and applicable laws and regulations.

The Sponsor shall monitor tasks delegated to other organizations/persons (Sponsor's oversight) e.g. contract research companies (CRO) or other consultants.

The Sponsor is responsible for developing a study plan and compile a clinical study report when the study is completed.

The Sponsor shall make sure that electronic systems used in the study are validated; that a Trial Master File is created; subjects' identities are coded so that reported data is coded but can be linked to the respective research person; that all essential study documentation is available in a safe place before, during and after the study according to applicable laws and regulations.

The Sponsor shall also make sure that the investigators have sufficient qualifications, enough resources are available at site, collect signed study plans from respectively responsible investigator and establish agreements with participating clinics.

It is the Sponsor's responsibility to check that there is an EC approval for the study, to register the study in a public database and assure that the study results are reported within one year.

All study deviations will be documented in the CRF to enable analysis and reporting by the Sponsor in the Study Report, or to the relevant regulatory authority(s), if applicable.

8 RISKS AND BENEFITS OF THE INVESTIGATIONAL MEDICAL DEVICE AND CLINICAL INVESTIGATION

8.1 Anticipated Clinical Benefits

Participation in this study will not directly benefit the subject nor will it alter the subject's course of care. However, information gained from the study may identify parameters that affect the hearing outcomes, which may be used to guide more effective and personal rehabilitation in the future.

8.2 Anticipated Adverse Device Effects

Not applicable, non-interventional study.

8.3 Risks Associated with Participation in the Clinical Investigation

Participation in the study presents no risk for the subject and does not alter the subject's course of care. Sensitive data concerning the subject's health is being handled in the study.

8.4 Risk Mitigation

All data collected will be pseudonymised and therefore the risk that any sensitive data will be disclosed to unauthorized persons is minimal. Registered post will be used when sending the non-opposition form signed by the investigator and questionnaire. For questionnaire, clinical personnel will complete header with subject identification code and request that no personal data is shared on this document, making it pseudo anonymised.

8.5 Risk-to-Benefit Rationale

The benefit of the clinical investigation of potentially identifying parameters that affect clinical hearing outcome and hence being able to guide more effective interventions in the future is regarded to outweigh the minimal anticipated risk for the subjects participating in the clinical investigation. We therefore consider it ethical to conduct the investigation.

9 STATISTICAL CONSIDERATIONS

9.1 General Considerations

Descriptive statistics will be derived for all data points. All analyses will be made on the full data set. All analyses will be presented as aggregated data without the possibility of identifying data from individual subjects.

Sentence recognition scores form the basis for most study endpoints. Missing test scores will be resolved with the study team. For example, if subjects can be assumed to have scored zero at 1-day or 1-month.

For the secondary endpoints such as longitudinal sentence test scores, logarithmic interpolation can be used for data missing for any given time-point. For missing fixed SNRs, logistic interpolation from present SNRs will be used. Longitudinal data for all subjects will be fit to the standard 1-day, 1-month, 3-month, 6-month, 1-year, 2-year, 3-year follow-up schema, with scores in quiet and 10 dB, 5 dB, 2 dB and 0 dB SNR. (NB certain levels are often omitted in standard clinical testing where the subject is known to be performing at ceiling or at floor for the condition.)

There is no criterion for termination of the study on statistical grounds.

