7.1.1 Design Rationale

The aim is to recruit all CI patients with a Nucleus device who have been evaluated since the centre's specific test battery was implemented in 2019. This includes some patients implanted as long ago as 2016. The centre implants approximately 25 eligible adult patients per year. As such therefore there is no bias in the selection of patients. Unilateral deaf or single-sided deaf CI recipients are excluded since natural hearing may interfere with the measure of performance of the implanted ear. Similarly, subjects who received bilateral cochlear implants will be included but their sentence recognition scores only considered for the first ear implanted up until they received the second implant.

Subjects with a cognitive impairment will also be included since the evaluation of cognitive function is one of the aims of the test battery.

The Toulouse centre has extensively studied early performance indicators of CI recipients, as well as looking at prognosis of performance in the long-term. Extension of the implications of the study findings to the long term is one of the exploratory objectives of the study, as is the subjective evaluation of performance by the recipients themselves.

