9.4 Sample Size Determination

Two scenarios with different underlying good/poor performer proportions were simulated (see figures 3 and 4): 50/50 and 40/60. $\geq 80\%$ power is obtained under both scenarios. Higher specificity and sensitivity would increase the power. Increasing the total number of subjects would also increase power.

[figure not shown]

Figure 4: Power calculations for a 40%/60% good/poor performer scenario.

Based on sample size calculations, a total of 30 eligible subjects are required to provide $>80\%$ power to reject the null hypothesis for the statistical test for the primary objective.

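### The longitudinal grid in 9.1 runs to 3 years for all subjects, but follow-up may end well before that and nothing bars filling scores past a subject's last test

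*Combined protocol and SAP*

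**What the plan says.** On the longitudinal analysis, section 9.1 says: "Longitudinal data for all subjects will be fit to the standard 1-day, 1-month, 3-month, 6-month, 1-year, 2-year, 3-year follow-up schema". It allows logarithmic interpolation for missing time points and sets no limit at the last observed test. Section 7.3.3.7 collects later scores where tests were done, from one month after activation to recruitment, and adds: "Dates of tests will also be collected to enable longitudinal extrapolation". The fourth endpoint in 9.2.3 is the set of scores from 1 day up to recruitment.

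On how long follow-up is, section 4.3 expects scores to 1-2 years where they exist. Section 7.1.1 says that "Extension of the implications of the study findings to the long term is one of the exploratory objectives of the study". It also uses bilateral subjects' scores for the first ear only, and only until the second implant. Under inclusion criterion 2 the second implant may come as little as 6 months after the first.

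On who is recruited, section 7.1.1 aims for every Nucleus patient evaluated since the test battery began in 2019, including some implanted in 2016, and states: "The centre implants approximately 25 eligible adult patients per year". Section 7.2.5 instead sets an order and a stop: "Recruitment shall start with the last subject that has undergone this procedure in the year 2021 and chronologically working backwards until recruitment targets are met". The target is 30 (9.4). In the first draw (7.3.1), "the number of subjects intended to be enrolled plus 20% (to account for non-responders) will be contacted".

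**The concern.** The grid promises more follow-up than the sample may have. Recruiting backwards from the end of 2021 and stopping at the target favours the most recent implants, which are the subjects with the shortest follow-up. A 3-year column for all subjects could then be completed only by carrying a curve past the last test.

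A value produced that way is a function of the subject's earlier scores. If it were related to the battery result or to SSQ12, the analysis would partly repeat the early finding under a long-term label. Section 4.3 wants to relate the learning trajectory to subjective performance, and 7.1.1 wants to extend the findings to the long term, so such a use is within the plan's stated aims.

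The sections also disagree without any assumption about dates: 1-2 years (4.3) against 3 years (9.1), interpolation (9.1) against extrapolation (7.3.3.7), and recruiting everyone (7.1.1) against stopping at the target (7.2.5).

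**Working it through.** **The plan's own figure.** Section 9.4 says that "a total of 30 eligible subjects are required to provide" more than 80% power. With sensitivity and specificity of 80% (7.2.3) and alpha 0.05 (9.3.1), exact power at 30 subjects is 94.1% (uncorrected chi-squared) or 87.2% (Fisher) for a 15/15 split, and 93.9% or 88.5% for 12/18. The claim of more than 80% reproduces, so 30 is taken as the stopping point.

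**Inputs.**
- Target: 30 subjects (9.4).
- First draw: 30 × 1.2 = 36 contacted (7.3.1).
- Rate: about 25 eligible implants a year (7.1.1).
- Order: backwards from the last 2021 surgery (7.2.5).
- Implant window: January 2016 to December 2021 (inclusion criterion 3).
- Recruitment date: not stated. The window closes in December 2021. Section 4.3 says the battery has been in routine use for 2-3 years and 7.1.1 dates it from 2019, which suggests 2021-2022. Recruitment in 2022 is therefore an inference, and the date is varied below.

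**Depth of the sample, D.**
- All patients in order join: 30/25 = 1.20 years, or 14.4 months.
- 30 of 36 join: 36/25 = 1.44 years, or 17.3 months.

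**Subjects who could have a score at Y years.** Let recruitment fall T years after 31 December 2021, with implants spread evenly over D. A subject implanted s years before that date has s + T years at recruitment and reaches Y if s ≥ Y − T. So

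n(Y) = 30 × max(0, D − (Y − T)) / D.

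Activation is taken to be at surgery, which slightly favours the plan. Each cell gives the number able to have a 2-year / 3-year score.

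| Sample | D (years) | T = 0 | T = 0.5 | T = 1 |
|---|---|---|---|---|
| 25 a year, all join | 1.20 | 0 / 0 | 0 / 0 | 5.0 / 0 |
| 25 a year, 30 of 36 join | 1.44 | 0 / 0 | 0 / 0 | 9.2 / 0 |
| 30 of the 75 implanted 2019-2021 | 3 | 10 / 0 | 15 / 5 | 20 / 10 |
| 30 spread over 2016-2021 | 6 | 20 / 15 | 22.5 / 17.5 | 25 / 20 |

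Examples:
- D = 1.44, T = 1, Y = 2: 30 × (1.44 − 1)/1.44 = 9.2.
- D = 6, T = 0.5, Y = 3: 30 × (6 − 2.5)/6 = 17.5, so 12.5/30 = 42% could not have a 3-year score.

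**When the 3-year point becomes possible at 25 a year.** T must exceed 3 − D, which is 3 − 1.44 = 1.56 years (36 contacted) or 3 − 1.20 = 1.80 years (30 contacted). Both fall after the middle of 2023.

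These counts are upper limits on observed scores. They ignore tests that were not done and the cut-off at a second implant, which removes later first-ear scores whatever the recruitment date.

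**The case against.** The strongest reply is that the depth of 14-17 months rests on one figure that other sections qualify. Section 7.2.3 reports that staff estimate 30 or more eligible patients in total, whereas 25 a year over 2019-2021 alone would give 75. If the usable pool is close to 30, working backwards nearly exhausts it, and the stop rule and the aim of recruiting everyone largely coincide. Some subjects would then have been implanted in 2016 and could have 3-year scores. This stands, and it is why the conclusion is conditional.

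It is also fair that filling is allowed rather than required, that fitting to a schema may mean no more than assigning tests to nominal visits, and that extrapolation appears in a single clause. No hypothesis in 9.3.3 names a 2- or 3-year score; 9.3.3.4 relates SSQ12 to SNR50 without giving a time point. So the harm is possible, not planned.

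What this does not answer is that no section stops filling at the last observed test and one section provides for going beyond it. Even the older pool leaves a sizeable share without a possible 3-year score.

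A reader might also infer that the fill must give impossible values. A log-time line through 60 at 1 day and 90 at 1 month has slope 30/ln(30) = 8.82 and gives 60 + 8.82 × ln(180) = 106 out of 100 at 6 months. The documents do not support that as a prediction. Those scores are classification cut-offs, not one subject's data, and no section specifies an unbounded two-point line. Interpolation between two observed scores cannot exceed 100.

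**Conclusion.** The point holds as a minor one. As written, the plan lets late scores be generated from early ones, and its sections disagree on the length of follow-up.

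The size depends on two things that the documents leave open, the recruitment date and the depth of the pool. At 25 eligible a year and recruitment within 2022, no subject could have a 3-year score and 0 to about 9 of 30 a 2-year score. At mid-2022, across the pools the documents allow, about 42% to 100% could not have a 3-year score; the lower figure assumes an even spread over 2016-2021. With that same pool, recruitment at the end of 2022 would lower it to 10/30 = 33%.

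A reader might go further and conclude that the sample will be almost entirely recent implants and that its 2- and 3-year scores will be extrapolated. The documents do not establish this: they give no recruitment date, they allow a smaller and older pool, and they permit filling without requiring it. The 1-month primary endpoint and the sample size are unaffected.

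**What to change.** - In 9.1 and 7.3.3.7, allow interpolation over time only between two observed tests in the same ear, and delete extrapolation beyond the last observed test. Logistic interpolation across SNR levels at a given visit is a separate matter.
- Report each time point only for subjects who reached it, with n shown.
- Reconcile 4.3, 7.1.1, 7.2.5, 7.3.3.7 and 9.1: one statement of expected follow-up, one recruitment rule (everyone evaluated, or stop at 30), and a long-term objective limited to the follow-up that the sample has. While doing so, correct 9.1's description of the longitudinal scores as secondary endpoints, since 9.2.2 says there are none.

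The cost is wording, and fewer late time points in an exploratory endpoint. No extra patients or tests are needed, and the change is sound whichever pool or recruitment date applies.
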